Current practice/treatment in local hospital (IVIG +Rituximab) and existing side effects

IVIG and rituximab combination therapy has not been used in local hospitals for the treatment of pemphigus. This is a pilot study in Hong Kong comparing the use of combination therapy with IVIG and Rituximab versus rituximab alone in the treatment of pemphigus. Ahmad *et al.*⁸ found that combination therapy with IVIG and rituximab in 10 patients with pemphigus with contraindications to systemic corticosteroid resulted in long-term sustained remission (> 6 years). Of note there were lack of adverse events, no infections, deaths or hospitalisations.

Criteria:

Ages Eligible for study : 18 years to 70 years (Adult, Older Adult), by the day of signing informed consent

Sexes Eligible for study : All

Inclusion Criteria:

- Written informed consent obtained from patient
- Ages Eligible for Study: 18 years to 70 years (Adult, Older Adult)
- Newly or recently diagnosed (less than 18 months) diagnosed pemphigus vulgaris or pemphigus foliaceus based on clinical features; histological features of acantholysis via skin or mucosal biopsy; and intercellular staining pattern of indirect immunofluorescence or serological detection of DSG 1 or DSG 3 by enzyme-linked immunosorbent assay (ELISA)
- Moderate to severe active disease, as defined by overall PDAI \geq 15 or skin involvement BSA \geq 5%.⁹ [Annex 1]
- Receiving standard-of-care oral prednisolone up to 1.5 mg/kg/day
- Women who are sexually active and not postmenopausal, agreement to remain abstinent or use 2 effective methods of contraception.
- Ability to comply with study protocol as deemed by investigator's assessment

Exclusion criteria:

- Age <18 or >70
- Pregnant women or nursing mother
- Already diagnosed pemphigus patients diagnosed > 18 months
- Non-consenting patients, or patient who cannot be followed up regularly
- Patient with history of serious allergy or anaphylactic reaction to monoclonal antibody treatment
- Severe heart failure (NYHA Class III or IV)
- Unstable angina or myocardial infarction within last 3 months or post-infarction heart failure
- Anaemia (haemoglobin $<10\text{g/dL}$), Neutropenia ($<1000/\text{mm}^3$), Lymphopenia ($<900/\text{mm}^3$), thrombocytopenia ($<100,000/\text{mm}^3$)
- Renal insufficiency eGFR <60
- Liver insufficiency of ALT/AST > 2 times normal limit range
- Positive test results for hepatitis C (HCV) serology at screening
- Blood test positive for HIV

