Statistical analysis of results will be done with IBM SPSS statistic program version 25. All tests of significance are two-tailed, and a P value of < 0.05 is considered to indicate statistical significance.

Primary outcome:

- 1) Percentage of participants who achieve relapse-free complete remission

Secondary Outcomes:

- 2) Time to protocol defined disease flare
- 3) Duration of complete remission, evaluated by the PDAI activity score [Baseline up to end of study]
- 4) Number of protocol defined disease flares
- 5) Time to initial complete remission, evaluated by the PDAI activity score [Baseline up to end of study]
- 6) Change in health-related quality of life as measured by the Dermatology Life Quality Index (DLQI) Score [Time Frame: Baseline, Week 4, 12, 24, 36, 48, 60, 72, 84, 96, 120, 144, 168, 192]
- 7) Occurrence of severe treatment adverse events (grade 3 or 4) based on common terminology criteria for adverse events (CTCAE), or death from any cause
- 8) Blood DSG 1 and 3 levels [Baseline week 0, week 4, 12, 20, 24, 36, 48, 60, 72, 96, 120, 144, 168, 192]
- 9) Blood lymphocyte level (CBC) [Baseline week 0, week 4, 12, 24, 36, 48, 60, 72, 96, 120, 144, 168, 192]
- 10) Blood CD19/20 mean B cell counts percentage [Time Frame: Baseline, week 4, 12, 20, 24, 36, 48, 60, 72, 96, 120, 144, 168, 180, 192]
- 11) Number of rescue therapy given

Baseline investigations prior to commencing therapy

General investigations:

- CBC
- Renal panel
- Liver panel
- Fasting Glucose/HbA1c
- Urine microscopy
- Urine pregnancy test in women of childbearing age
- Serum immunoglobulins for IgA deficiency
- B cell (CD19/20) enumeration

- DSG 1, 3 ELISA

Infective screen:

- HepBs Ag, Anti-HBs Ab, anti-HepBc total antibodies
- Anti-HCV IgG
- Anti HIV 1 and 2 (if indicated)
- CXR
- Interferon-gamma release assays

Patients who have positive IGRA test results

As Tuberculosis (TB) is endemic in Southeast Asia, should Interferon-gamma release assays result be positive, the patient will be reviewed by infectious diseases specialist and need treatment of latent TB treatment prior to starting Rituximab. Patients will need to have completed at least 4 weeks of isoniazid or treatment with other TB medications, before commencement of the study.

Patients who are HepBs Ag positive, or HepBs Ag negative and anti-HepBc Ab – positive

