Steroid sparing agents such as azathioprine or MMF are reduced to half the dose once the patient is successfully recruited into the study and will be tapered and stopped upon commencement of the study.

Relapse/ failure to achieve complete remission

- Additional infusion of weekly rituximab 375mg/m² BSA weekly x 4 will be given at the time of relapse/ or if patient fails to achieve complete remission 2 months from last dose of rituximab. After initial induction phase for both arms, the time between subsequent doses of rituximab for treatment of relapse should be at least 2 months apart.

Rituximab infusion protocol:

Pre-medications

- Paracetamol 1000mg one hour before Rituximab infusion
- IV Piriton 30 minutes before Rituximab infusion
- Methylprednisolone 100mg IV or Hydrocortisone 100mg IV half hour before Rituximab infusion

Preparation:

- IV Rituximab is prediluted at a dose of 500mg in 500ml of 0.9% normal saline (i.e. 1:1 dilution, 1 mg/ml)
- Initial infusion rate starts at a rate of 50mg/hr (50ml/hr)
- If no hypersensitivity/anaphylaxis reaction occurs, increase infusion rate in 50mg/hr (50 ml/hr) increments every 30 minutes

- Maximum infusion rate is 400 mg/hr (400 ml/hr)
- Subsequent infusion: start at rate of 100mg/hr (100 ml/hr), increase 100mg/hr (100 ml/hr) increments every 30 minutes
- Monitor temperature, BP HR, respiratory rate and SpO2 every 30 minutes

Adverse effects

Infusion-related:

- Fever, chills/rigors
- Injection site pain
- Nausea and vomiting
- Asthenia, headache, myalgia, giddiness
- Rhinitis, throat irritation
- Pruritus, rash
- Risk of infections
 - ** Infections including urinary tract infections, pneumonia, pneumocystic pneumonia, herpes simplex, herpes zoster, cytomegalovirus infection. Lung and brain abscess. Severe hypogammaglobulinaemia, and high-dose immunosuppressants may be possible risk factors for systemic infections
- Neutropenia
- Pyelonephritis
- Haemolytic anaemia
- Toxic epidermal necrolysis
- Parkinsonism

Intravenous immunoglobulins (IVIG)

Treatment dosage: 2g/kg over 2-5 days

Infusion Protocol

0 min	: 50ml/hour
15 min	: 75ml/hour
30 min	: 100ml/hour
45 min	: 125ml/hour
60 min	: 150ml/hour
75 min & beyond	: 180ml/hour

For patients receiving IVIG for first time, wait 30mins before 1st increase. Infusion rate should be less than 0.27ml/kg/hour in the following groups of patients:

- Renal insufficiency
- Diabetes mellitus
- ≥ 65 years of age
- Sepsis
- Paraproteinaemia

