- Patients receiving nephrotoxic drugs

* In patients with renal impairment, or risk factors for thromboembolic disease or fluid overload, consider infusing IVIG at a dose of 0.4g/kg/day for 5 days (total dose 2g/kg) at a rate of less than 0.27ml/kg/hour, and in not less than 8 hours.

- Restoring immune regulation when B cells are being re-populated to normal levels
- Synergy and interactions of immune pathways and inflammatory system
- IVIG regulated B cell functions and suppression of production of pathogenic autoantibodies through idiotype network interactions

During IVIG infusion:

- Hourly parameters, watch out for tachycardia, hypertension, dyspnoea, chest tightness, facial flushing, fluid overload
- In the event of an adverse reaction:
 - Inform the doctor
 - Decrease the infusion rate to previous level or stop the infusion if symptoms persist
 - Do not increase the rate any further
 - Paracetamol for fever, chills, headache or myalgia and antihistamines for pruritus or urticaria
 - Restart at a slower rate when symptoms have resolved, and consider premedication prior to future infusions
 - Report as adverse reaction to a blood product

Anaphylactic reaction

Syncope (dizziness), dyspnoea, hypotension

- Stop the infusion immediately
- Resuscitate if necessary
- Oxygen therapy, IV antihistamines (benadryl 50mg) and other appropriate measures

Other potential adverse events:

- Acute renal failure
Elderly patients and those with diabetes mellitus or impaired renal function are at risk
- Arterial thrombosis (stroke and myocardial infarction) and venous thrombosis (deep vein thrombosis and pulmonary embolism) following IVIG have been reported. Patients at risk of thrombotic events may include those with a history of atherosclerosis, multiple cardiovascular risk factors, advanced age, impaired cardiac output, and/or known or suspected hyperviscosity.⁶
- Transmission of blood-borne agents such as Hepatitis B/C and HIV
- Acute meningitis syndrome
This may occur 48 to 72 hours after IVIG.
Signs and symptoms include severe headache, nuchal rigidity, drowsiness, fever, photophobia, nausea and vomiting.
May occur more frequently with high dose (2g/kg) IVIG treatment.

- Cutaneous reactions
Reports of eczematous reactions and other varied morphologies. One report of erythema multiforme.

The British Associate of Dermatologists guidelines for management of pemphigus vulgaris 2017 ¹

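### Renal, glucose and immunoglobulin tests are scheduled only at baseline, although the IVIG rate conditions and named risks concern changes that can arise on study; laboratory-only change would be found only by unscheduled testing

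*Protocol*

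**What the plan says.** Under the heading "Baseline investigations prior to commencing therapy" the protocol lists, among other tests, a renal panel, "Fasting Glucose/HbA1c" and "Serum immunoglobulins for IgA deficiency". None of the three is given a later time point anywhere in the document.

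Other bloods are scheduled on study. The secondary outcomes give explicit weeks, for example "Blood DSG 1 and 3 levels [Baseline week 0, week 4, 12, 20, 24, 36, 48, 60, 72, 96, 120, 144, 168, 192" and "Blood lymphocyte level (CBC) [Baseline week 0, week 4, 12, 24, 36, 48, 60, 72, 96, 120, 144, 168, 192", and a similar list for CD19/20. AST and ALT are repeated at intervals of three months or less, under the hepatitis B heading.

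Three other parts of the protocol bear on the tests that are not repeated:

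- The IVIG infusion protocol sets a lower rate for several groups, including patients with renal insufficiency and patients with diabetes. A note to it asks for slower dosing to be considered in renal impairment.
- The IVIG adverse events include acute renal failure, with the comment "Elderly patients and those with diabetes mellitus or impaired renal function are at risk".
- The rituximab adverse effects say: "Severe hypogammaglobulinaemia, and high-dose immunosuppressants may be possible risk factors for systemic infections".

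The exclusion criteria include "Renal insufficiency eGFR <60". Diabetes is not an exclusion. No eligibility criterion mentions the IgA result.

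**The concern.** The protocol's own infusion rule and risk statements refer to patient states that can change during treatment, but its schedule measures those states once, before treatment starts. Patients with eGFR below 60 are excluded at entry, so renal insufficiency relevant to the IVIG rate would mostly arise later. Both arms take prednisolone on a taper of three or six months, with intravenous steroid before each rituximab infusion, so a glucose status recorded before that exposure need not hold through it. Immunoglobulins are taken for one stated purpose, IgA deficiency, and not in connection with the infection risk that the protocol itself links to low levels.

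Two things are at stake. First, a patient whose renal function or glucose changes without symptoms could continue on IVIG with no scheduled result to show it. Second, laboratory-detected harms would depend on who happened to be tested. The trial is open-label, so investigators may test one arm more readily than the other, and a difference in laboratory abnormalities could then reflect testing rather than treatment. The combination has not been used for pemphigus in local hospitals, so safety information is one of the main things this pilot can deliver.

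**Working it through.** No sample size, power or error rate is involved. The check is a count of infusion weeks against blood-test weeks.

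**1. Arm 2 infusions (Arm 2 text and table).** IVIG weeks are 0, 4, 8, 12, 16, 20 and 24 (7 cycles), then 30, 38, 48, 60 and 76 (5 cycles) for patients disease-free at week 24: 7 + 5 = 12. The text bullets name six IVIG weeks up to week 24, so the stated total of seven needs the table's week 0. Rituximab weeks are 1 to 8, then 12, 16, 20 and 24: 8 + 4 = 12. Both reproduce the stated totals of 12 and 12.

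**2. IVIG cycles after baseline.** Full course: 12 − 1 = 11, the last at week 76. A patient who does not go on to the five later cycles: 7 − 1 = 6, the last at week 24. Relapse treatment could extend exposure.

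**3. Scheduled blood tests after baseline (secondary outcomes and baseline list).**

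| Test | After baseline, whole study | Of these, by week 76 |
|---|---|---|
| CBC | 12 | 7 |
| DSG 1 and 3 | 13 | 8 |
| CD19/20 | 14 | 8 |
| Renal panel | 0 | 0 |
| Fasting glucose/HbA1c | 0 | 0 |
| Immunoglobulins | 0 | 0 |

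**4. Overlap with existing draws.** CD19/20 is drawn at weeks 4, 12, 20, 24, 36, 48, 60 and 72 within this period. Of the 11 later IVIG weeks, 4, 12, 20, 24, 48 and 60 coincide with a draw: 6 of 11. The other five are 8, 16, 30, 38 and 76. If the three tests followed the CD19/20 weeks, the latest earlier draw before each of these would be 8 − 4 = 4, 16 − 12 = 4, 30 − 24 = 6, 38 − 36 = 2 and 76 − 72 = 4 weeks old. The oldest would therefore be 6 weeks. As the protocol stands, the only scheduled result predates week 0, so it is at least 24 weeks old at the week 24 cycle and at least 76 weeks old at the last one.

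**5. Arm 1 duration.** The text places 4 + 4 + 4 = 12 rituximab doses from weeks 0, 24 and 52, the last at week 55. The table places 4 + 4 + 2 + 2 = 12, the last at week 77. The totals agree and the end dates do not. Arm 1 has no IVIG, so neither date bears on the IVIG rate conditions; both bear on how long rituximab continues with no repeat immunoglobulin test.

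**The case against.** The strongest reply is that the trial has other ways to notice harm. CTCAE grade 3 or 4 events and deaths are a secondary outcome, all infusions are in-patient, patients are observed hourly during IVIG, visits are monthly and then three-monthly, and nothing forbids an unscheduled test. This stands. A reader might infer that renal, glucose and immunoglobulin harms would go unseen; the documents do not support that. What lacks planned detection is change that shows only in the laboratory.

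Other stronger readings also fail:

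- *That the rate rule has no data to act on.* Baseline glucose/HbA1c identifies existing diabetes, the baseline renal panel informs the first cycle, and age and nephrotoxic drugs need no laboratory test. Only new renal or diabetic change is without a scheduled check.
- *That the renal condition can apply only to patients who deteriorate on study.* The infusion section gives no eGFR cut-off, so a patient with mildly reduced function at entry might already fall under it.
- *That the IVIG concern runs for 77 weeks, or touches every patient.* Week 77 comes from the Arm 1 table. IVIG is given only in Arm 2, about 10 patients, and beyond week 24 only to those disease-free at that point.
- *That hypogammaglobulinaemia is a listed treatment harm.* It is named only as a possible risk factor for infection.
- *That serial IgG would explain a difference in severe infection.* With about 10 patients per arm, and infused product contributing to the Arm 2 level, it could not settle that.
- *That the IgA result can have no bearing on entry.* Severe immunodeficiency is excluded and the investigator may exclude for concomitant disease. The criteria simply do not mention the IgA result.

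It can also be said that testing frequency is a matter of preference. That would carry more weight if the protocol left all on-study bloods open. It does not: it fixes weeks for some tests and gives none for tests that bear on its own rate conditions. A safety-test schedule is protocol content, so the statistical analysis plan, which is not at hand, would not be expected to supply it.

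**Conclusion.** The point holds in a limited form. The renal panel, glucose/HbA1c and immunoglobulins have no scheduled measurement after baseline, while the protocol ties the IVIG rate to renal insufficiency and diabetes, names acute renal failure as an IVIG risk, and names severe hypogammaglobulinaemia as a possible risk factor for infection. In Arm 2 this leaves 6 to 11 IVIG cycles per patient after baseline with no scheduled renal or glucose result, if the planned course is followed without relapse treatment. In both arms, about 20 patients, immunoglobulins are scheduled once in four years of follow-up.

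The consequence is that new laboratory-only changes would be found only by unscheduled testing, and that such testing may differ between arms. Differential testing is a possibility that follows from the open-label design; the documents give no figure for its size. Nothing here affects the primary outcome, and clinically apparent severe events remain capturable. This is a cheap improvement to safety data.

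**What to change.** Add the renal panel, glucose and immunoglobulins to the existing DSG/CBC/CD19/20 blood time points in both arms, with the sample taken before the infusion on IVIG weeks. Using the same weeks in both arms makes laboratory findings comparable between them, and it reconciles the blood schedule with the IVIG rate conditions and the named risks. Six of the 11 later IVIG weeks already have a CD19/20 draw; the other five are planned in-patient admissions, if the sponsor wishes to sample then as well.

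Two reconciliations belong in the same amendment. The purpose of the baseline IgA test should be reconciled with the eligibility criteria, which do not mention its result. The Arm 1 text (last rituximab dose at week 55) should be reconciled with the Arm 1 table (week 77). What any result should mean for eligibility, infusion or treatment is for the sponsor to decide; no clinical threshold or rule is proposed here.

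The cost is a short amendment and a small laboratory charge for about 20 patients, with no extra visits.

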Cost effectiveness is an important issue and while combination of IVIG and rituximab has been advocated, the cost of such treatment is substantial and whether it poses any benefit over rituximab alone, or with other more conventional immunosuppressive agents, has not been established. Both treatment approaches have been previously published in high impact journals.^{3,5} In this study, we aim to evaluate the efficacy and safety of early use of rituximab with or without IVIG in patients with moderate to severe pemphigus using protocols that were similar to those previously published. Apart from complete remission and adverse effects, we will also aim to measure the impact of health care economics and in doing so, assess the cost and benefits of both treatment arms.

Hypothesis:

IVIg in combination with Rituximab is more superior than Rituximab alone in the treatment of moderate to severe pemphigus.

Methods:

Prospective multi-centre, randomised open-label trial

Patients will be randomised to two treatment arms: Rituximab alone or Rituximab + IVIG

Aim to recruit ~10 patients per arm (20 patients in total)

Patients will be reviewed monthly for the first 6 months then 3 monthly in clinic thereafter, follow up will be up to 4 years.

When patient enrolment is confirmed and written consent is obtained, the investigator will open the envelop sequentially and patient will receive the treatment plan stated on the allocation slip. Patient will be randomised to either rituximab arm or rituximab and IVIG arm. The random allocation sequence will be generated using computer-generated random numbers. Randomisation will be to the two arms of the trial in 1:1 ratio. The allocation sequence will be printed on paper slip. A non-study related research assistant will put the slips in to sequentially numbered, opaque, sealed envelopes.

Arm 1 (Rituximab alone arm):

- Rituximab infusion 375mg/m² body surface area (BSA) weekly for 4 weeks from baseline
- Rituximab infusion 375mg/m² BSA weekly for 4 weeks at week 24
- Rituximab infusion 375mg/m² BSA weekly for 4 weeks at week 52
- A total of 12 doses of rituximab will be given in 55 weeks
- If a patient relapses after initial rituximab infusion, further rituximab infusion 375mg/m² BSA weekly for 4 weeks can be given at time of relapse/or if patient fails to achieve complete remission 2 months from last dose of rituximab.

Week 0, 1, 2, 3	Rituximab (375mg/m ²)
Week 24, 25, 26, 27	Rituximab (375mg/m ²)

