Week 52, 53	Rituximab (375mg/m ²)
Week 76, 77	Rituximab (375mg/m ²)

Arm 2: (Rituximab and IVIG arm):⁵

- Rituximab (375 mg/m² BSA) once a week for 4 weeks (week 1, 2, 3) and
- Week 4: Rituximab + IVIG 2g per kg
- Week 5, 6, 7: Above treatment repeated for 2nd cycle, infusion of rituximab (375 mg/m² BSA) once a week for 4 weeks (week 5, 6, 7) and
- Week 8: Rituximab + IVIG 2g/kg
- In week 12, 16, 20, 24 patients received a single infusion of rituximab (375 mg/m² BSA) plus infusion of 2g/kg IVIG
- Thus in 24 week period patients received a total of 12 infusions of rituximab and 7 infusions of IVIG
- If a patient was clinically free of disease at end of 24 weeks, additional infusions of IVIG will be given at week 30, 38, 48, 60 and 76
- A total of 12 doses of rituximab will be given and 12 cycles of IVIG will be given
- If a patient relapses or flares during the treatment, four infusions of rituximab at 375mg/m² BSA will be given at 1-weekly interval will be administered and IVIG 2g/kg will be given at week 4 of treatment after week 32

Week 0	IVIG 2g/kg, divided total dose given over 2-5 days
Week 1, 2, 3	Rituximab (375mg/m ²)
Week 4	Rituximab (375mg/m ²) + IVIG
Week 5, 6, 7,	Rituximab (375mg/m ²)
Week 8	Rituximab (375mg/m ²) + IVIG
Week 12	Rituximab (375mg/m ²) + IVIG
Week 16	Rituximab (375mg/m ²) + IVIG
Week 20	Rituximab (375mg/m ²) + IVIG
Week 24	Rituximab (375mg/m ²) + IVIG
Week 30	IVIG
Week 38	IVIG
Week 48	IVIG
Week 60	IVIG
Week 76	IVIG

For both study arms:

- After initial induction phase for both arms, the time between subsequent doses of rituximab for treatment of relapse should be at least 2 months apart.
- Patients will be followed up for 4 years starting from baseline visit

IVIG and Rituximab

Ahmed et al.⁵⁻⁷ has published data and protocol combining rituximab and IVIG. The theory behind this is that IVIG:

- Contains antibodies directed against B-cell-activating factor belonging to tumour necrosis factor family
- Exact mechanism by which Rituximab and IVIG are effective in induction of prolonged sustained clinical, serological and immuno-pathological remission in patients is not clearly understood – After destroying autoantibody-producing pathogenic B cells, the repopulating B cells do not produce autoantibodies. It is conceivable that in a microenvironment that more closely resembles normal physiology and homeostasis, IVIG could initiate the process of immune restoration.

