- Signs of active infection on CXR
- Positive interferon gamma release assay Quantiferon or T.Spot TB test: must be treated with at least 4 weeks post initiation of isoniazid or other TB therapy
- Inherited or acquired severe immunodeficiency
- History of malignancy
- Patient with active severe infection (excluding fungal infections of the nail), which has required antibiotic treatment within 2 week prior to study enrolment
- Infection requiring hospitalisation or intravenous antibiotic treatment within the last 8 weeks prior to enrolment

- Past history of osteomyelitis, or fasciitis, septic arthritis within the last one year
- Patients with drug induced pemphigus. A thorough medication history will be taken to rule out drug induced pemphigus including D-penicillamine, angiotensin-converting enzyme inhibitors, angiotensin receptor blockers and cephalosporins
- Evidence of any new or uncontrolled concomitant disease that in the investigators' judgement would preclude the patients participation
- Patients with history of allergy or adverse events to IVIG or rituximab treatment¹⁰
- Treatment with intravenous immunoglobulins, plasmaphoresis within the last 8 weeks prior to randomization
- Previous treatment with rituximab or any monoclonal antibody inducing profound lymphopenia
- Treatment with live or attenuated vaccine within the last 28 days prior to randomization

Admission and follow up:

- All infusions will be performed as in-patient procedure of prospective hospital and all patients are to be follow up monthly at out-patient of the prospective Queen Mary Hospital dermatology out-patient clinic
- Patients will be followed up monthly for the first 6 months, then followed up for every 3 months up to 4 years starting from baseline visit

Outcome measures:

Patients' serum will also be taken for desmoglein antibodies and levels will be charted and independent samples t-test will be used to compare the collected data between the two groups. Homogeneity of the treatment groups at baseline will be analyzed using the Mann–Whitney U test and Wilcoxon signed-rank test for independent and dependent variables. The Kaplan-Meier method will be used to estimate the likelihood of reaching the endpoint of relapses or flares within the drug infusing period based on the intention-to-treat population, defined as all patients who has received at least one dose of study medication. The log-rank test will be used to compare time-to-event curves between treatment groups.

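### HIV is an exclusion based on a blood result, but the infective screen makes the HIV test conditional and does not define the condition, so undiagnosed infection can pass screening

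*Protocol*

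**What the plan says.** Under Exclusion criteria, the protocol excludes a patient with "Blood test positive for HIV". The criterion is a laboratory result. It does not mention history or suspicion, and it does not say who is tested or when.

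The tests themselves are listed under "Baseline investigations prior to commencing therapy". In the infective screen of that section the HIV item reads "Anti HIV 1 and 2 (if indicated". No section defines when the test is indicated or who decides, and no other section requires an HIV test before rituximab.

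The hepatitis C exclusion, in the same list, is worded differently: "Positive test results for hepatitis C (HCV) serology at screening". The matching anti-HCV test in the infective screen carries no condition. The hepatitis B markers, chest X-ray and interferon-gamma release assay are unconditional too.

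On exposure, Arm 1 states "A total of 12 doses of rituximab will be given in 55 weeks" and Arm 2 states "A total of 12 doses of rituximab will be given and 12 cycles of IVIG will be given". The section on relapse or failure to achieve complete remission adds "Additional infusion of weekly rituximab 375mg/m² BSA weekly x 4 will be given at the time of relapse", and extends this to patients not in remission two months after their last dose. Both severity groups follow a prednisolone taper.

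**The concern.** An exclusion that depends on a test result works only if the test is done. Here an untested patient can neither meet the criterion nor be cleared of it. The patients most likely to go untested are those whose infection nobody suspects, and a screening test exists to find them.

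The stake is mainly safety. Both arms receive repeated B-cell depletion with corticosteroid. The protocol's own list of rituximab adverse effects includes pneumocystis pneumonia, cytomegalovirus infection, and lung and brain abscess, and it names high-dose immunosuppressants as a possible risk factor for systemic infection.

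A lesser consequence concerns attribution. The protocol lists transmission of blood-borne agents, HIV among them, as a potential adverse event of IVIG. If a patient in the IVIG arm with no baseline result later tests positive, the trial data cannot show whether the infection was already present. The screen secures that baseline for hepatitis B and C but not for HIV.

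**Working it through.** The check is mainly a comparison of passages. The arithmetic only gives scale.

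**1. Exclusion against test, item by item (Exclusion criteria; Infective screen)**

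| Item | Role in eligibility | Test in the infective screen |
|---|---|---|
| Hepatitis C | Excluded on serology at screening | Unconditional |
| Hepatitis B | Not excluded; managed by marker and DNA status | Unconditional |
| Tuberculosis | Positive assay needs at least 4 weeks of treatment first | Unconditional |
| Chest X-ray | Excluded if signs of active infection | Unconditional |
| HIV | Excluded on a positive blood test | Conditional, condition undefined |

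HIV is the only conditional item in the infective screen.

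**2. Could another exclusion close the gap?** The exclusion list contains lymphopenia below 900/mm³, "Inherited or acquired severe immunodeficiency", recent serious infection, and concomitant disease that the investigator judges would preclude participation. These may catch some advanced cases. None of them identifies undiagnosed HIV in a patient who has none of these features. The gap is therefore a patient who is undiagnosed, has no apparent indication for testing and meets none of these criteria.

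**3. Scheduled rituximab doses**
- Arm 1, bullets: 4 + 4 + 4 = 12.
- Arm 1, table: 4 + 4 + 2 + 2 = 12. Its timing differs from the bullets, which is a separate matter; the total agrees.
- Arm 2, table: 8 doses in weeks 1 to 8, plus 4 at weeks 12, 16, 20 and 24, = 12.

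The stated 12 reproduces in both arms. It is a scheduled total, not a ceiling: one relapse or non-remission course gives 12 + 4 = 16, and two give 12 + 8 = 20.

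**4. Chance of at least one affected patient.** The documents give no prevalence, so this is an assumption. Let q be the proportion of candidates with unsuspected infection who would pass screening, and n = 20 (the planned total, Methods). The formula is 1 − (1 − q)^n.
- q = 0.001: 1 − 0.999^20 = 0.020, with 20 × 0.001 = 0.02 expected patients.
- q = 0.01: 1 − 0.99^20 = 0.182, with 20 × 0.01 = 0.2 expected patients.

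**5. Timing.** The Methods have the envelope opened once enrolment is confirmed and consent obtained. The heading of the test list ties it to the start of therapy, not to allocation. The text therefore does not expressly require the screening results before allocation.

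**The case against.** The best defence is that the two passages can be read together. The HIV criterion, unlike the hepatitis C one, does not mention screening, and the test list mirrors that difference. On this reading the protocol excludes anyone who has a positive result, whether on record or from an indicated test, and an untested patient breaches nothing. This stands as a reading of the words: it would go too far to call such a patient an eligibility violation or to call the text a flat contradiction. But it rescues the wording and leaves the safety exclusion ineffective in unsuspected infection. The other exclusions narrow the gap, as shown, without closing it.

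It is also fair to say that an affected patient is unlikely. At the lower assumed prevalence there is a 98% chance that none of the 20 is affected, and the 18% comes wholly from the upper end of the assumption.

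A reader might infer that a late diagnosis would force a withdrawal and shift an arm's remission rate by 10 points. The documents do not support this:
- No section requires withdrawal on a later HIV diagnosis.
- The population defined under Outcome measures for the Kaplan-Meier analysis is everyone who received at least one dose, so a patient diagnosed after dosing meets that definition.
- If one of 10 patients were removed, the shift would be (x − 10)/90 for a responder and x/90 for a non-responder, where x is the number of responders. From 8/10 this gives 7/9 (−2.2 points) or 8/9 (+8.9 points). Ten points is the maximum, reached only at 1/10 to 0/9 or 9/10 to 9/9.

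**Conclusion.** The point holds as a mismatch between an eligibility criterion and the screening list meant to serve it. As written, a patient with undiagnosed HIV, no indication for testing and none of the other exclusions can be randomised and given 12 scheduled rituximab doses, plus four per further course, with prednisolone.

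This conclusion rests on the text alone and needs no assumption about prevalence. The 2% to 18% depends entirely on the assumed 0.1% to 1%; it shows scale and is not an estimate for this population. The sample size and the planned analysis are not affected. Nor does the unseen SAP matter here, because eligibility and screening belong in the protocol. It is a limited defect, worth correcting because it concerns patient safety and is cheap to remove.

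**What to change.** Reconcile the Exclusion criteria with the infective screen before allocation starts, by one of two routes:

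- **Make the screen supply the result.** Remove the condition on the HIV item, so that every candidate has a result from the screening blood already drawn, and state that it must be available before the envelope is opened.
- **Make the exclusion match the screen.** Reword it to known HIV infection, define when the test is indicated, and obtain the ethics committee's agreement that undiagnosed infection may go undetected.

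Either route makes the text consistent; the choice belongs to the sponsor and the ethics committee. The first costs about 20 assays, pre-test counselling and a short amendment. The second needs only the amendment and the committee's agreement, but leaves the safety gap open by decision. Whether the consent form already covers HIV testing cannot be seen, because the consent pages are not in the material reviewed.
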